2.2 Secondary Objectives

- 2.2.1** To compare treatment related toxic effects of thoracic radiotherapy regimens in patients with limited stage small cell lung cancer.
- 2.2.2** To compare response rates, failure-free survival and toxicity of thoracic radiotherapy regimens in patients with limited stage small cell lung cancer.
- 2.2.3** To compare rates of local relapse, distant metastases and brain metastases with these regimens.
- 2.2.4** To compare patients' quality of life between these treatment regimens in terms of their physical symptoms, physical functioning and psychological state.
- 2.2.5** To describe the patterns of use of thoracic intensity modulated radiation therapy (IMRT) in patients with limited stage small cell lung cancer.
- 2.2.6** To examine blood-based biomarkers of response and resistance to cisplatin (or carboplatin) and etoposide.
- 2.2.7** To evaluate the correspondence between increases in plasma ProGRP concentrations and disease progression/recurrence.

2.2.8 To evaluate the potential for plasma ProGRP concentrations at baseline, after each cycle of chemotherapy and at first evaluation following completion of chemotherapy to predict PFS and OS.

2.2.9 To evaluate the correspondence between longitudinal decreases in plasma ProGRP concentrations and clinical response.

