C-1728 30610 Treatment and Response Form	Every 2 cycles during protocol treatment (including the non-protocol cycle of chemo, if applicable).
C-660 Solid Tumor Evaluation Form	
Report CT scan reports	
C-1729 Adverse Event Form	Every cycle during protocol treatment
C-1742 Confirmation of Lost to Follow-up Form	Follow form directions.
C-1730 Follow-up and Response Form	After the end of protocol treatment submit every 3 months for 2 years, then every 6 months for 3 years, then every year for an additional 5 years until progression. After progression submit only the C-1730 every 6 months to report survival, new malignancy, and non-protocol treatment data. Report new malignancy on the C-1001.
C-660 Solid Tumor Evaluation Form	
Report CT scan reports	
C-1001 New Malignancy Form	

This study will use NCI Common Terminology Criteria for Adverse Events (CTCAE) version 3.0 for routine toxicity reporting on study forms. However, CTCAE version 5.0 will be used for **serious** AE reporting through CTEP-AERS as of April 1, 2018; see [Section 16.0](#).

* Use CALGB Remarks Addenda (C-260) if additional comments are necessary or additional writing space is needed.

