* Pre-registration labs may be used for day 1 of cycle 1 tests if obtained within 14 days prior to day 1 of Cycle 1. For subsequent cycles labs may be obtained within 48 hours prior to day of treatment. Patients receiving treatment on a Monday may have labs obtained within 72 hours.

** Weight must be recorded weekly during thoracic radiotherapy

*** At least every 3 months for 2 years, then every 6 months for 3 years, then every year for an additional 5 years until disease progression. After progression, follow every 6 months for survival and new malignancy.

† The dose of chemotherapy need not be changed unless the calculated dose changes by ≥ 10%.

A See [Section 13.5.3](#) for CT instructions. Note that a CT scan made as part of the PET-CT is acceptable if it meets all the criteria in Section 13.5.3. Any CT scan that does not meet these requirements must be repeated.

B Obtain on days 1 and 8 of each cycle.

C Obtain MRI or CT of brain prior to initiating prophylactic cranial irradiation.

D Obtain 6 and 12 months from the start of treatment, then as clinically indicated.

Ψ For those patients who consent to participate in the substudies.

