In the initial stage of the study, eligible patients will be randomized to arms 1, 2 and 3 with probability ratio of 1:1:1. A blocking design with 30/30/30 patients will be used to compare toxicity between the experimental arms. Specifically, after 30 patients have been accrued to each experimental arm, the Alliance Statistics and Data Center will computerize and analyze all treatment related toxicities and report findings to the study team and the DSMB. For the 60 patients treated by experimental regimens, permutation t test will be used to compare toxicity severity scores between experimental arms. If the 2-sided p value of the permutation test is less than 0.05, a decision will be made to drop the experimental arm with higher toxicity; otherwise, the study will continue and adverse events will be analyzed again after 20 additional patients have been treated in each experimental arm. For the 100 patients treated by experimental regimens so far, if statistically significant difference of adverse events is found between the experimental arms, a decision will be made to drop the

experimental arm with higher toxicity; otherwise, the study will continue after 20 additional patients have been treated in each experimental arm. For the first 140 patients treated by experimental regimens, the experimental arm with the highest cumulative numerical toxicity score will be discontinued following review by the study team and the DSMB.

A notice will be broadcast to all Alliance and CTSU institutions for the discontinuation of an experimental arm. In the initial stage of the trial, while the toxicity profiles of treated patients are being evaluated, the study accrual will not be suspended. In the second stage, the study will proceed with the remaining experimental arm and the standard treatment arm with 1:1 allocation.

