15.1.3 Secondary Endpoint

Secondary endpoints will include complete and partial response rates, failure-free survival, local tumor progression according to RECIST criteria, and rates of distant metastases and intracranial metastases. Failure free survival is the time from randomization to death of all causes or disease progression, whichever comes first. Second primary tumors will not be viewed as disease progression.

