15.4 Analysis Plan Including Plans for Formal Interim Analysis

Both short term and long term toxic effects of therapy will be captured and monitored closely. Severe toxic events will be reported and monitored as per NCI guidelines for clinical studies (e.g., CTEP-AERS). These data will be critical in the assessment of each of the treatment regimens. In addition, the Alliance DSMB will perform a formal review of the available data at each of its semiannual meetings. This review will include both acute and late toxicity.

After discontinuing one of the experimental arms with worse toxicity profile, in the second stage of the study, the first formal interim analysis for efficacy will occur once 78 deaths are observed in the remaining study arms. After that, formal interim analyses will be conducted annually, with the final analysis at year 8.5, corresponding to approximately 140, 213, 292, 374, 437 and 483 deaths. The trial is subject to stopping early for either superiority or inferiority of the experimental relative to the standard arm if either arm was markedly superior in terms of overall survival. The main reason is that if both arms were roughly equal in terms of overall survival, the final conclusion might be to recommend the experimental arm for future use because of less toxicity or more convenience. Using S+SeqTrial [83], we will construct two-sided symmetric monitoring boundaries in the spirit of O'Brien and Fleming [84]. To maintain overall 1-sided alpha level of 0.025 for each boundary and be conservative in the initial looks, we will truncate alpha level at 0.0005 for the first look and at 0.0025 for other interim looks [85]. The final analysis at 8.5 years after study activation will conclude superiority (inferiority) of the remaining experimental arm to the standard arm if the p-value of a one-sided log rank test for superiority (inferiority) is less than 0.0220. The following table displays the operating characteristics, including power, average study size, stopping probabilities under true hazard ratios of 0.75, 1.0, 1.3, and 1.5. The exact performance of the study design, especially under different allocation ratios in the first and the second stage of the study, will be investigated using simulation.

Hazard Ratio ($\lambda_1/\lambda_{2/3}$)	Expected Number of Deaths	Prob. to Reject $H_0: \lambda_1 / \lambda_{2/3} = 1$ (Power)	Early Stop Prob. for Superiority	Early Stop Prob. for Inferiority
0.75	354	0.8763	0.0000	0.6348

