1.0	479	0.0250	0.0081	0.0081
1.3	377	0.8106	0.5357	0.0000
1.5	245	0.9928	0.9385	0.0000

The Alliance DSMB will review the data available from the trial at each of its semiannual meetings. This will include toxicity, disease recurrence and survival information. The DSMB will determine which of its biannual meetings most appropriately fits the protocol-dictated one-year formal interim analysis. This determination will be based on a recommendation of the study statistician. In determining whether the trial should be continued, the DSMB will consider the results at each interim analysis, as described above. The DSMB will use its discretion in weighing the combined impact of treatment-related morbidity, disease recurrence and overall survival.

Overall survival (OS) is defined as the time between randomization and death from all causes. Overall survival curve will be estimated by the Kaplan-Meier method. The primary analysis is to test the survival benefit of the experimental therapy over the standard therapy using stratified log rank test in the intent-to-treat (ITT) population. Six stratification factors, including Gender, Weight loss, ECOG Performance Status, Radiotherapy Technique, Radiotherapy Start Time, and Chemotherapy Backbone, have been used in randomization. As a total of 144 stratum have been defined by these factors and many of the stratum may end up of small number of patients. For the primary analysis, the stratified log rank test will only stratify on patient subgroups defined by Performance Status (0 vs 1/2) and Chemotherapy Choice (entry prior to the option to use carboplatin, choice of carboplatin among those patients for which this is an option, and choice of cisplatin among those patients for which this is an option). Cox's proportional hazards model will be used to estimate hazard ratio between treatments with and without adjusting for other prognostic factors.

Failure free survival (FFS) is the time from randomization to death of all causes or disease progression, whichever comes first. In this study, second primary tumors will not be viewed as disease progression. FFS will be analyzed in a similar manner to overall survival (OS).

The rates of local relapse, distant metastases and brain metastases with the regimens will be evaluated using logistic regression with treatment and other prognostic factors in the model.

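### Local, distant and brain failure rates are compared by logistic regression with no time point and no rule for death, censoring or first failure at another site

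*Combined protocol and SAP*

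**What the plan says.** Objective 2.2.3 reads "To compare rates of local relapse, distant metastases and brain metastases with these regimens". Section 15.1.3 names the endpoints as "local tumor progression according to RECIST criteria, and rates of distant metastases and intracranial metastases". Section 15.4 then gives the method: "The rates of local relapse, distant metastases and brain metastases with the regimens will be evaluated using logistic regression with treatment and other prognostic factors". RECIST settles what counts as a local event. Nothing in these sections settles when the event is counted, or what happens to patients who die without it, are censored, or fail first somewhere else.

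The plan is more careful elsewhere. Overall survival (OS) and failure-free survival (FFS) are times from randomization, and for the primary analysis "the stratified log rank test will only stratify on patient subgroups defined by Performance Status (0 vs 1/2) and Chemotherapy Choice". Where Section 15.6 uses logistic models for survival-type outcomes, it attaches a two-year horizon.

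On timing, Section 15.3 gives six years of accrual and a minimum of 2.5 years of follow-up. Section 15.4 places annual looks after the first one, "with the final analysis at year 8.5, corresponding to approximately 140, 213, 292, 374, 437 and 483 deaths".

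On disease data, Section 7.0 says "After progression, follow every 6 months for survival and new malignancy", and Section 6.1 says "After progression submit only the C-1730 every 6 months to report survival, new malignancy, and non-protocol treatment data". The calendar in Section 7.0 lists brain imaging before registration and before prophylactic cranial irradiation (PCI), and none in post-treatment follow-up.

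**The concern.** A logistic model needs a yes/no outcome. Without a horizon, that outcome is whether a failure was seen by the data cut-off, so it depends on how long each patient was alive, failure-free and observed. With equal survival in the two arms this harms interpretation but does not bias a test of no difference. With the survival gain that the trial is designed to detect, patients on 70 Gy spend longer at risk, and the crude odds ratio reflects that as well as any effect on failure at the site.

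Two conclusions are at stake. An unchanged hazard of failure at a site can appear as a higher rate on 70 Gy, and a real reduction can be diluted. Section 1.1 makes better local control part of the case for higher-dose regimens, so readers will look to this comparison to explain the survival result. If the counting rule is chosen after the data are seen, that explanation will carry little weight.

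**Working it through.** **1. The plan's own figures.** Section 15.3 gives exponential survival with medians of 23 and 29.9 months, 303 patients per arm, 72 months of accrual and 30 more months of follow-up. Assume uniform accrual, so potential follow-up is uniform from 30 to 102 months. The proportion dead is 1 − [exp(−30k) − exp(−102k)]/(72k).
- 45 Gy, k = ln2/23 = 0.0301: 83.5%.
- 70 Gy, k = ln2/29.9 = 0.0232: 75.7%.
- Deaths: 303 × (0.835 + 0.757) = 482.4, against 483 stated. This is about 80% of 606 patients.
- Power: Φ(√483/2 × ln 1.3 − 1.96) = 82.2%, against 81.9% stated.

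**2. What the crude proportion measures.** Let h be the hazard of first failure at a site, and c the hazard of everything that pre-empts it (death without failure, first failure elsewhere). The proportion failing at the site by time t is h/(h+c) × [1 − exp(−(h+c)t)]. The crude proportion averages this over follow-up of 30 to 102 months.

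**3. Inputs.** The documents give no planning rates by site, so these are assumptions. Section 15.6 uses 40% for two-year FFS (at the biomarker mean). Applied to the 45 Gy arm, this gives a total first-failure hazard of −ln(0.40)/24 = 0.0382 per month. The site is given 20%, 30% or 42% of it. On 70 Gy, the hazard of the other failures and deaths is divided by 1.3.

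**4. Worked case, site share 30%.** On 45 Gy, h = 0.0115 and c = 0.0267.
- Missing horizon: the 45 Gy proportion is 0.30 × 0.60 = 18.0% at 24 months, 20.5% at 30 months and 29.4% at 102 months. The crude figure is 26.8%, which is the risk at no stated time.
- Equal site hazard: on 70 Gy, c = 0.0267/1.3 = 0.0206 and the crude figure is 30.4%. The odds ratio is 1.20 although the hazard ratio is 1.
- Site hazard also cut by 25%: the 70 Gy figure is 24.3%. The odds ratio is 0.88 although the hazard ratio is 0.75.

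**5. Rejection rates.** Simulated with 10,000 trials per scenario, two-sided 0.05, unadjusted tests, independent exponential times, full detection and no other loss. The crude test is the Wald test of the log odds ratio; the cause-specific test is the log-rank test. The planned survival gain is present throughout.

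| Setting | Equal site hazard: crude vs cause-specific | Site hazard cut 25%: crude vs cause-specific |
|---|---|---|
| Tied to 40% two-year FFS (step 3) | 14-19% vs 5% | 8-14% vs 31-56% |
| Few relapse-free deaths (one quarter of the OS hazard; site hazard 0.0081 or 0.0218 per month) | 7-10% vs 5% | 30-39% vs 49-76% |

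The upper site hazard in the second row gives a crude 45 Gy rate of 61.5%. That is above the 42% local relapse quoted for this regimen in Section 1.1, so this row is a range check rather than a forecast. With all hazards equal, both tests reject in 5%.

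**6. Absolute risk.** A Gray-type test, which compares cumulative incidence, rejects in 6-21% at equal site hazard over all settings run, and in about 14-16% under step 3. Its power with the joint benefit is 9-49%.

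**7. Missing death rule.** Take an equal site hazard of 0.02 per month and relapse-free death at the full OS hazard. Counting deaths without failure as non-events gives 37.5% (45 Gy) vs 42.4% (70 Gy). Excluding those patients gives 86.2% vs 83.5%. The direction reverses, and the text permits either. The setting is harsh, with exp(−24 × 0.0501) = 30% failure-free at two years, so it shows direction rather than size.

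**The case against.** The strongest reply is that a rate is naturally read as an absolute risk. If fewer patients die, more live long enough to fail at a given site, and a test that detects this is not in error. That stands: the Gray-type test moves almost as far as the crude one. A reader might take 14-19% as a false-positive rate, and it should not be called that. What remains is that absolute risk and hazard answer different questions, and the plan does not say which it compares or at what time.

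Other stronger readings also fail:
- *The crude test rejects in up to a quarter of trials.* A simulated 25% does arise, but only with a site hazard of 0.0218 and relapse-free death at the full OS hazard. That leaves exp(−24 × (0.0218 + 0.0301)) = 29% failure-free at two years before any other-site failure, against 40% in Section 15.6.
- *70 Gy would look worse even when it is better on both counts.* With the joint benefit, the crude test was significantly against 70 Gy in under 1% of trials. The risk there is a missed benefit.
- *Staggered entry biases the comparison.* The two arms were allocated equally in stage one, and after that "the study will proceed with the remaining experimental arm and the standard treatment arm with 1:1 allocation", so entry times balance.
- *An early stop would leave follow-up too short.* Section 15.4 does not tie the site analysis to an OS boundary, and Section 15.3 promises 2.5 years of follow-up without condition. Only if site data were cut at the 374-death look (month 78, follow-up 6 to 78 months) would (24 − 6)/72 = 25% of patients have under two years.
- *The endpoint is wholly undefined.* Local progression follows RECIST, and the final analysis is set at year 8.5.

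It is also fair that an equal site hazard with a survival gain suits distant or brain failure better than local relapse, because Section 1.1 expects survival to improve through local control. These are secondary endpoints with no stated power or error rate.

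**Conclusion.** The concern holds as a gap that should be closed, not as a threat to the trial's main result. Section 15.4 applies logistic regression to crude proportions that have no horizon and no rule for death, censoring or other-site failure, and no other section supplies them.

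The practical cost falls mainly on power. If 70 Gy lowers the site hazard by 25% and lengthens survival as planned, the crude comparison would usually miss what the cause-specific hazard comparison finds about a third to a half of the time or more. Part of that loss also reflects the choice of absolute risk over hazard.

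The sizes rest on assumed site shares, constant hazards, independent failure and death times, and full detection. The direction rests only on survival differing between the arms. Nothing here touches OS or FFS.

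**What to change.** In Section 15.4, replace the logistic regression sentence with wording such as:

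> Local, distant and brain failure will each be analysed as time from randomization to first failure at that site; every site found at the same evaluation counts. Death without failure and first failure at another site are competing events. Patients alive without failure are censored at the last evaluation of that site. Cumulative incidence at 2 years by arm, allowing for competing events, will be reported with the cause-specific hazard ratio from a Cox model stratified as in the primary analysis. Prognostic factors in the model are fixed before data lock.

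State in Section 15.1.3 that the endpoint is first failure by site, because disease forms stop at progression. Any logistic regression that is kept should be supportive, at a fixed horizon within the 2.5-year minimum follow-up, with a stated rule for death.

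The change needs no new visits or forms, but it is more than a wording edit:
- The endpoint becomes narrower than objective 2.2.3, since later failures at other sites are not counted.
- No brain imaging is listed after the pre-PCI scan, so brain failure is clinically detected. Say so, define before data lock what counts as an evaluation of the brain, and do not let a chest CT date stand as a brain-free assessment.
- The hazard ratio and the two-year risk can point in different directions, so both must always be shown.

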15.5 Logistics and Accrual

An estimated 174,000 patients will be diagnosed with lung cancer in 2006. Small cell lung cancer comprises approximately 16-20% of all lung cancer, and accounts for 22% of all lung cancer cases accrued to cooperative group clinical trials. According to the National Cancer Data Base, 42% of staged patients had limited stage disease in 2000, and 11,000 to 14,000 new cases of limited stage small cell lung cancer are expected annually. The total accrual goal is 729 patients. To complete accrual in 6 years, the accrual rate will be approximately 10 patients per month (120 patients per year). We anticipate this trial to be opened by all major Alliance and RTOG sites, and several additional adult cooperative groups including SWOG and ECOG have

agreed to participate in this trial. The accrual goal should be achievable given the track record of accrual to limited stage small cell lung cancer trials in these Groups. Given the uncertainty in clinical practice regarding the optimal thoracic radiotherapy regimen in limited stage small cell lung cancer, we expect that the question addressed by this study will lead to a high level of interest and participation. In addition, there are few competing cooperative group, industry, or institutional studies in this patient population.

15.6 Correlative Studies (CALGB 150712)

In the main treatment study, a total of 303 patients will be randomized to the standard control arm (arm A) and the remaining experimental arm (arm B or arm C, depending on the toxicity data from an initial cohort, the more toxic experimental arm will be dropped). These patients will be followed for disease progression and survival for at least 3 years after enrollment. All patients will be invited to join the correlative science substudies. Samples from consenting patients will be collected at baseline (before treatment initiation), day 21 (pre-chemotherapy), at first follow-up after completion of all protocol treatment, and at the time of disease recurrence. The laboratory data, including measures of all biomarkers described in the protocol, will be sent to the Alliance Statistics and Data Center, where the laboratory data will be merged with the clinical data and analyzed by Alliance statisticians.

Power Analysis for the First Correlative Science Substudy (Section 10.1.1):

The primary objectives of this first correlative science substudy are (i) to test whether higher-dose, accelerated radiation therapy (arm B or C) will cause a larger rise in circulating markers of endothelial damage than hyperfractionated and accelerated radiotherapy (arm A), and (ii) to determine whether the baseline biomarker profile, or changes in the profile during treatment, correlate with clinical outcome as judged by objective response rate, progression free survival, and overall survival.

With allowance of 20% patient loss due to consent, ineligibility, and specimens of poor quality, we assume that 264 patients on arm A and 264 patients on arm B/C will provide evaluable circulating biomarkers for final analysis. With regards to the first primary objective, we assume the transform of biomarker count difference between post-treatment initiation and baseline follows approximately a normal distribution so that a 2-sample t test would be appropriate. At a 2-sided significance level of 0.05, the study has 90% power to detect a 0.274 standard deviation of cell count difference between the two treatment arms on log scale. With regards to the second primary objective, for the purpose of power analysis, the correlation of the biomarker (baseline or change scores of post-initiation of treatment against baseline) with response rate, 2-year FFS and 2-year OS will be tested for each arm using logistic regression with a single continuous predictor. At a 2-sided significance level of 0.05, the study has at least 90% power to detect a 6% increase of response rate from 80% at the mean of the biomarker to 86% at one standard deviation above of the mean. Similarly, the study has at least 90% power to detect an 11% increase of 2-year FFS from 40% at the mean to 51% at one standard deviation above of the mean, to detect an 11% increase of 2-year OS from 50% at the mean of a biomarker to 61% at one standard deviation above of the mean.

Power Analysis for the Second Correlative Science Substudy (Section 10.1.2):

The primary objective of the second correlative substudy is to evaluate the correlation of several serum markers at baseline or their changes against baseline with response rate (RR), failure free survival (FFS), and overall survival (OS) in small cell lung cancer. They include neuron-specific enolase (NSE), carcinoembryonic antigen (CEA), BB isoenzyme of creatine kinase (CK-BB), angiogenic factors Interleukin 8 (IL-8) and Vascular Endothelial Growth Factor (VEGF), stem cell factor (SCF), granulocyte-macrophage-colony stimulating factor (GM-CSF), and tumor

hypoxia marker osteopontin. The correlation tests are considered exploratory and the Type I errors will not be adjusted for multiple comparisons.

It is assumed that 230 randomized patients (70%) on each arm will consent and provide valid measures for these biomarkers. These biomarkers are concentration in the blood. The baseline measures and the change at different time points – day 21; at first follow-up after completion of all protocol treatment; and at the time of disease recurrence – against baseline are continuous variables. For the purpose of power analysis, logistic regression with a single continuous predictor will be used to test a measure's correlation with RR, 2-year FFS, and 2-year OS, separated by study arm. At a 2-sided significance level of 0.05, the study has at least 90% power to detect a 6% increase of response rate from 80% at the mean of the biomarker to 86% at one standard deviation above of the mean. Similarly, the study has at least 90% power to detect a 12% increase of 2-year FFS from 40% at the mean to 52% at one standard deviation above of the mean, to detect a 12% increase of 2-year OS from 50% at the mean of a biomarker to 62% at one standard deviation above of the mean.

Power Analysis for the Third Correlative Science Substudy (Section 10.1.3):

Most studies of proGRP have reported that approximately 70-80% of patients have increased levels of proGRP in their serum or plasma. The primary endpoint examines the correlation of increases in the plasma proGRP levels with changes in disease status. This strategy is based on the analyses performed for tumor markers used for monitoring and approved by the FDA, such as CA19-9, CA15-3, CA125 and CEA. Changes above a cutoff are compared for to clinical evaluation of stable disease vs. progression. In the secondary studies, the correlation of decreases in proGRP level will be compared to stable disease vs. regression and/or remission designations. The data is analyzed as concordance of 2 X 2 table of clinical outcome vs. a defined change in cutoff levels. For proGRP, 3 levels will be evaluated initially a) the percent increase that is 2.5 times the assay's observed total percent coefficient of variation (CV), b) a percent change that is 2.5 times the assay and biological variation, and c) a change of >25% based on changes used with other cancer biomarkers. The change in disease state is evaluated per sequential pair and per patient. Secondary analyses can determine whether a different cutoff functions better than these 3 cutoffs. Individual patients will be evaluated by following their sequential proGRP values and their clinical status via tables and graphs.

Based on the numbers of patients and samples sufficient for these evaluations for other monitoring biomarkers as submitted to and approved by the FDA, it is recommended that between 150 and 200 patients be enrolled in this study. A sample size of approximately 150 and 200 patients will provide a sufficient number of evaluable patients with 95% confidence and 80% to 90% statistical power for evaluating the association of the change in ProGRP assay values and change in disease status.

For the primary study and the secondary studies of the relationship of proGRP levels at baseline and at each round of chemotherapy and at the end of therapy will be analyzed as defined above.

Analytic Methods

All data from eligible patients with evaluable measures of the biomarker of interest will be included in final analysis. A 2-sided significance level of 0.05 will be used for all tests.

Descriptive statistics will used to characterize biomarker count or distribution over time and changes against baseline. The change of biomarker count or mean between treatment arms will be tested using a 2-sample t test on a transformed scale such as the use of t test is appropriate. If the normal assumption is violated, Wilcoxon rank sum test, a nonparametric test, will be used. As supplementary analysis, the difference of biomarker count and mean change will be modeled using generalized linear model using appropriate link function.

The correlation of the baseline measure or the change of the biomarker measure relative to baseline with response rate (RR) will be evaluated using logistic regression [86] with and without adjusting for significant confounding variables at baseline. The correlation of the biomarker with failure free survival (FFS) and overall survival (OS) will be evaluated using Cox's proportional hazard model [87] for time to event data without and with adjusting for confounding variables. These analyses will reveal whether the baseline biomarker or its change against baseline during treatment is predictive to RR, FFS, or OS, or whether the correlation is dependent on which treatment is given. In the pooled analysis of all patients on the treatment arms, the interaction between treatment and baseline or change score of the biomarker will be tested to evaluate the predictive value of the biomarker to different treatments.

If a continuous biomarker is significantly correlated with FFS or OS, an optimal threshold for classifying patients into subgroups will be identified by searching the dichotomized level of the continuous predictor at which yields the maximal log rank statistic. Both the raw p-value from the log rank test as well as the adjusted p-value from the maximal log rank statistic [88], which takes the randomness of the maximally selected cutoff point into account, will be provided. Kaplan-Meier curves [89] will be used to describe survival difference for different subgroups of patients classified by predictive biomarker at its optimal cutoff point.

To assess the correspondence between increases in plasma ProGRP and disease progression or recurrence, patients will be considered evaluable if they have at least five blood draws, one at baseline and the remaining draws at 3, 6, 9 and 12 months, respectively with the corresponding scans at those time points. Patients with CR, PR, and SD will be grouped together as non-progressive disease for the statistical analysis. Since each patient contributes a unique set of visit pairs to the data, this must be controlled by using techniques developed for generalized linear models. GENMOD procedure in SAS will be used to obtain the estimates of the concordances. The relationship between the concordance estimate C and the parameter estimate b is given by $C = (1 + e^{-b})^{-1}$. 95% confidence limits will be determined for all concordance proportion.

To evaluate the ability of ProGRP at baseline, after each cycle of chemotherapy and at first evaluation post-treatment, patients will be grouped into two different groups based on their ProGRP concentrations. At each of those intervals, they will be grouped as negative if (ProGRP \leq 50 pg/mL) or as positive if (ProGRP $>$ 50 pg/mL). In addition, changes in ProGRP concentrations starting at baseline and after the first or second dose of chemotherapy will also be explored. The log-rank test will be used to determine if the PFS for patients with positive values (or changes) are different from the negatives.

